APPENDIX A. IMPUTATION AND ANALYSIS STEPS FOR SENSITIVITY ANALYSIS OF THE PRIMARY VARIABLE

The following represents an outline of the planned methodology for the multiple imputation procedure for the sensitivity analysis of the primary OCS response variable. Minor deviations from this outline can be addressed in the discussion of the results in the CSR. In the situation that more significant updates are warranted, changes will be addressed in a SAP amendment to be finalized prior to database lock.

Step 1: Seed generation.

The seed generation utilized the code below, resulting in a seed (49476) that will be used in the analysis after unblinding.

```
data seed;
  seed = int(time());
  put seed=;
  call symput('seed', left(seed));
run;
```

Step 2: Classify patients with missing data.

Patients in this study will be partitioned into the following 3 categories:

1. ET0; patients who completed all 24 weeks of treatment
2. ET1; patients who withdrew early from treatment but remained in the study contributing post-treatment follow-up data through week 24
3. ET2; patients who withdrew early from treatment but elected not to remain in the study through week 24

Step 3: Imputation of missing data.

Missing values for OCS dose (continuous) at week 24 and at visits in which earlier OCS doses were missing will be imputed. The missing OCS dose will be imputed based on measurements observed at previous visits and treatment group, assuming data are missing at random (MAR). The resulting observations at week 24 will be categorized as per the primary endpoint.

If the pattern of missing data is monotonic, the MONOTONE method in PROC MI will be used for imputation with a linear regression technique.

```
proc mi data=&indata out=&outdata nimpute=10 seed=&seed;
  class treatment;
  monotone regression (week4=treatment base /details);
  monotone regression (week8=treatment base week4 /details);
  monotone regression (week12=treatment base week4 week8 /details);
  monotone regression (week16=treatment base week4 week8 week12 /details);
  monotone regression (week20=treatment base week4 week8 week12 week16 /details);
  monotone regression (week24=treatment base week4 week8 week12 week16 week20 /details);
  var treatment base week4 week8 week12 week16 week20 week24;
run;
```

If the pattern of missing data is not monotonic, the MCMC MONOTONE method can be selected to transform the missing data pattern to a monotonic missing data structure by filling in missing values for earlier visits that have lower rates of missing data (ie, MCMC MONOTONE as a preliminary step, to be followed by application of the MONOTONE method in PROC MI).

```
proc mi data=&indata out=&outdata nimpute=10 seed=&seed;
  mcmc impute=monotone NBIter=2000 NIter=10000;
  var base week4 week8 week12 week16 week20 week24;
  by treatment;
run;

proc mi data=&outdata out=&outdata2 nimpute=1 seed=&seed;
  class treatment;
  monotone regression (week4=treatment base /details);
  monotone regression (week8=treatment base week4 /details);
  monotone regression (week12=treatment base week4 week8 /details);
  monotone regression (week16=treatment base week4 week8 week12 /details);
  monotone regression (week20=treatment base week4 week8 week12 week16/details);
  monotone regression (week24=treatment base week4 week8 week12 week16 week20/details);
  var treatment base week4 week8 week12 week16 week20 week24;
  by _imputation_;
run;
```

After this step, 10 datasets with complete data have been created.

Step 4: Re-run the primary analysis model.

Percent change from baseline and the corresponding 5-level response variable will be computed based on the imputed dose values at week 24. The proportional odds model will be fitted to the complete set of data for each of the 10 imputed datasets using the same covariates that were used for the primary analysis.

Step 5: Multiple imputation and associated combining rules applied to propagate imputation uncertainty (Little and Rubin 2002).

The output datasets from Step 4 will contain inferential statistics for each imputation iteration. The SAS[®] procedure PROC MIANALYZE will be used to generate an overall p-value and 95% CI for the odds ratio.

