2.3. Sample Size and Power Considerations

The primary efficacy variable and endpoint for this study is the percent reduction in the daily OCS dose during weeks 20 to 24 as compared with the dose at the end of the optimization phase. The study will be considered positive if the measure meets statistical significance at the respective predefined significance level. A statistically significant effect of reslizumab over placebo, as measured by the primary efficacy variable, is required to establish the efficacy of reslizumab treatment.

The sample size was calculated based on the following assumptions:

- Categorical reduction in OCS dose after 24 weeks of treatment will have the following distribution for the placebo group (based on [Bel et al 2014](#)):
 - 10.9% percent of subjects will have 90% to 100% reduction
 - 7.9% percent of subjects will have 75% to <90% reduction
 - 14.8% percent of subjects will have 50% to <75% reduction
 - 10.8% percent of subjects will have 0% to <50% reduction
 - 55.6% percent of subjects will have no reduction, loss of asthma control, or discontinuation from study drug
- The overall odds ratio between reslizumab and placebo based on proportional odds model will be 2.63
- Alpha level of 0.05

Based on the above assumptions, a sample size of 76 subjects per group will provide 90% power to detect a significant effect of reslizumab over placebo on the probability for a higher categorical reduction of OCS dose.

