6.2.3. Sensitivity Analyses for the Primary Variable

The following list of sensitivity analyses are pre-specified for this study, with an aim toward assessing the robustness of the primary efficacy results:

- The primary analysis with control variables (age and OCS dose) based on data recorded in the IRT (as randomized). This analysis will only be performed if the number of discrepancies between data recorded in the IRT and the clinical database are sufficiently large (eg, 5% of total population).
- Per-protocol: analysis of the primary endpoint, based on the PP analysis set.
- Additional analysis including data collected after early withdrawal from treatment.

- If a patient elects to withdraw from treatment (or is discontinued from treatment by the investigator), every attempt will be made to continue the assessments subsequent to his/her withdrawal from the study. If the patients agrees to remain in the study, they will continue to receive study prednisone treatment for the remainder of their participation in the study.
- In this analysis, patients will be categorized according to the percent dose reduction at 24 weeks regardless of whether they withdrew early from treatment or completed treatment. For patients who withdraw early and for whom the sponsor fails to retrieve data after withdrawal despite all attempts to contact the patients, multiple imputation will be performed to determine the categorization according to the percent dose reduction at 24 weeks. The multiple imputations will use the post withdrawal data observed for patients who withdrew early and for which the sponsor succeeded to retrieve the data. The methodology and algorithm used for imputations will be detailed in [Appendix A](#).
- “Tipping point” multiple imputation: analysis of the primary endpoint to assess deviations from missing at random (MAR). The details regarding this analysis are provided in [Appendix B](#).

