APPENDIX B. TIPPING POINT ANALYSIS

The tipping point analysis evaluates several combinations of imputed missing data values until the analysis reaches a “tipping point” or point at which a particular combination of imputed missing data changes the study conclusions, as summarized by its p-value. This is a sensitivity analysis utilizing multiple imputations under the missing not at random (MNAR) assumption, and will only be conducted if a significant result ($p \leq 0.05$) is observed as part of the primary analysis. If the sensitivity analysis reveals that the tipping point consists of unreasonable values, then the robustness of the study results is supported. This is in accordance with the recommendation discussed in the "Prevention and Treatment of Missing Data in Clinical Trials Report" ([National Research Council 2010](#)).

The following represents an outline of the planned methodology for the “tipping point” multiple imputation sensitivity analysis of the primary response variable (OCS dose). Minor deviations from this outline can be addressed in the discussion of the results in the CSR. In the situation that more significant updates are warranted, changes will be addressed in a SAP amendment to be finalized prior to database lock.

Imputations will be performed for the missing OCS dose at week 24 and the resulting observations will be categorized as per the primary endpoint. OCS dose will be imputed for patients who discontinued treatment prior to the endpoint of the study. Multiple imputation and associated combining rules will be applied to propagate imputation uncertainty (see [Appendix A](#) for additional details). In the following analysis, the OCS dose in the control group will be imputed assuming that missing data are MAR. For the treatment group, the OCS dose will be imputed in the same manner, but then a constant shift (>0) will be added to the imputed values to allow for MNAR. In the treatment group, this shift will be progressively increased and the process repeated until the treatment effect is no longer significant at the 5% level. The value of the shift parameter at which the treatment effect is no longer significant is called the “tipping point”.

The tipping point analysis will be performed according to the following steps.

1. Missing values will be imputed assuming MAR in both treatment groups using the multiple imputation procedures described in [Appendix A](#) (Steps 1-3). This process will be repeated 10 times.

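### SAP Appendix A imputes week-24 OCS dose in mg by unbounded normal regression, which produces negative doses and thins the lowest response category in two sensitivity analyses

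*SAP*

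**What the plan says.** SAP Appendix A, Step 3, treats dose as a continuous quantity in mg: "Missing values for OCS dose (continuous) at week 24 and at visits in which earlier OCS doses were missing will be imputed". The method for a monotone pattern is that "the MONOTONE method in PROC MI will be used for imputation with a linear regression technique". The week-24 statement is "monotone regression (week24=treatment base week4 week8 week12 week16 week20 /details". Neither it nor any other statement in the appendix carries a minimum, a maximum, rounding, a transformation or predictive mean matching. A non-monotone pattern first goes through a normal-theory MCMC step and then the same regressions.

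Step 4 works on the raw draw: "Percent change from baseline and the corresponding 5-level response variable will be computed based on the imputed dose values at week 24". The categories in SAP 6.2.1 have hard edges. The best ends at 100% reduction, the lowest requires no decrease (or loss of control, or discontinuation), and any decrease above 0% moves a patient up one level. For this sensitivity analysis SAP 6.2.3 sets discontinuation aside: "patients will be categorized according to the percent dose reduction at 24 weeks regardless of whether they withdrew early from treatment or completed treatment".

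The patients without post-withdrawal data, and so in need of imputation, are Appendix A's group ET2: withdrawn from treatment and not followed through week 24. Appendix B reuses the same draws for the tipping point: "Imputations will be performed for the missing OCS dose at week 24 and the resulting observations will be categorized as per the primary endpoint". It adds a growing shift in mg to the reslizumab draws.

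**The concern.** Prescribed doses in this trial lie on a coarse grid (SAP Table 3) that ends at 0, and the dose is meant to be held stable from week 20 to week 24. A patient who could not be tapered sits at baseline; a fully tapered patient sits at 0. A normal regression in mg respects neither point. It also gives patients on 5 mg and on 40 mg the same residual SD, although a given error in mg is a far larger percentage for the former.

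At stake is how far the two multiple-imputation checks on the primary result can be read as tests of the five-level endpoint, and whether the tipping-point value keeps a clinical meaning.

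**Working it through.** **1. The plan's own figure.** Appendix A states none, so the design distribution was checked first. Inputs from SAP 2.3: placebo 10.9, 7.9, 14.8, 10.8 and 55.6%; odds ratio 2.63; 90% power; alpha 0.05 (two-sided in SAP 4.3). Multiplying the cumulative placebo odds by 2.63 gives reslizumab 24.3, 13.5, 19.3, 10.7 and 32.3%. The Whitehead formula is n per arm = 6(z_α/2 + z_β)² / [ln(OR)² (1 − Σp̄³)], with p̄ the mean of the two arms in each category:

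- 6 × (1.960 + 1.282)² = 63.0
- ln(2.63)² = 0.935
- 1 − Σp̄³ = 0.902
- n = 63.0 / (0.935 × 0.902) = 74.7, so 75 per arm

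That is within one patient of the stated 76. Power at 76 is 90.5% by formula and 89.9% by simulation.

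**2. What the code implies without simulation.** Let a draw be normal with mean m and SD s.

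- If m equals baseline, P(draw < baseline) = Φ(0) = 0.5 whatever s is. Half of such patients leave the lowest category. P(draw = baseline) = 0.
- If m = 0, P(draw < 0) = 0.5 whatever s is.
- The lowest category does not vanish, because draws above baseline still fall in it.

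**3. Simulation.** Appendix A was run with 76 per arm, dose paths following Table 3, proper parameter draws and 10 imputations (60 trials for the odds-ratio runs). Assumed, because the documents do not give them:

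- baseline mix: skewed or uniform over 5-40 mg
- share imputed: 5, 10 or 20%
- dropout: unrelated to dose (MCAR), or three times likelier while the dose is not yet reduced (MAR)
- placebo share with no decrease on dose alone: 25, 40 or 55.6%
- non-responders sitting 2.5 mg above baseline: 0-20%

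| Placebo no-decrease share | Dropout | Lowest category among imputed patients, Appendix A / truth |
|---|---|---|
| 55.6% | MCAR and MAR | 0.52-0.61 |
| 40% | MCAR and MAR | 0.54-0.65 |
| 25% | MAR | 0.53-0.66 |
| 25% | MCAR | 0.70-0.83 |

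Negative doses were 7-17% of imputed values, and none equalled baseline. At the 55.6% share the >0% to <50% category rose from about 4-9% to 32-35%.

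Other assumptions gave the same picture. With 12% placebo and 8% reslizumab dropout under MAR, 17-20% of draws were negative; the placebo lowest category was 11% against a true 21% in one scenario and 21% against 48% (ratio 0.44) in another. With stronger dose-related dropout, 7-10% were negative and one placebo result was 33% against 73% (ratio 0.45).

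**4. Size at trial level.** With 12% and 8% dropout, about 0.12 × 76 = 9.1 and 0.08 × 76 = 6.1 patients are imputed. In the 48% scenario the net loss from the lowest category is 9.1 × (0.48 − 0.21) = 2.5 placebo patients and 6.1 × (0.27 − 0.12) = 0.9 reslizumab patients, out of 152. Odds ratios from the grid:

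| Scenario | Full data | Appendix A |
|---|---|---|
| 55.6%, MCAR, 10% imputed | 2.58 | 2.52 |
| 55.6%, MAR, 10% | 2.56 | 2.51 |
| 40%, MAR, 10% | 2.74 | 2.68 |
| 25%, MAR, 10% | 2.54 | 2.54 |
| 55.6%, MAR, 20% | 2.74 | 2.60 |

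Under stronger dose-related dropout the shifts reached 2.58 to 2.39 (about 10% imputed) and 2.81 to 2.47 (about 20%). Significance differed from full data in 0-8% and 8-12% of trials respectively.

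**5. Tipping point.** Take baseline b and an imputed dose of −d. The shift must exceed d + 0.1b before that patient leaves the top category, against 0.1b for a real dose of 0. The part d only brings an impossible dose back into range.

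**The case against.** Most of the opposing case concerns size, and it stands.

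- The primary analysis counts early withdrawals as nonresponders (SAP 4.4, 6.2.2) and uses none of these draws.
- Protocol 4.5.1 makes the week-24 OCS dose a priority assessment after discontinuation, so the imputed group may be small.
- The rank-sum analysis in SAP 6.3.2.2.3 gives withdrawals the worst rank and is unaffected. Appendix B runs only if the primary result is significant.
- Moving dropouts out of the lowest category is partly the design under SAP 6.2.3. Only the excess is a fault.
- A negative dose has an obvious home in the top category, and Appendix A allows minor deviations. The missing mass at baseline is the more substantive fault.
- Not every real dose lies between 0 and baseline on the grid. The post-burst dose is 2.5 mg above the pre-burst dose (SAP 2.1.4.1), and the endpoint is a mean of daily doses.

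A reader might take the SAP 2.3 figure, "55.6% percent of subjects will have no reduction, loss of asthma control, or discontinuation from study drug", as proof that over half of placebo patients sit exactly at baseline. It is not: it pools three reasons, so the share with no decrease on dose alone is lower and unknown. That is why 25-55.6% was examined.

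A reader might also infer that these checks are worthless or flatter reslizumab. Neither follows. Few patients are involved, and the odds ratio moved towards 1 or not at all in the odds-ratio results reported.

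**Conclusion.** The fault holds as a defect in two sensitivity analyses. That draws can be negative and cannot equal baseline follows from the code itself. In simulation, negative doses were about 7-20% of imputed values. The lowest category among imputed patients fell to roughly 0.5-0.65 of its true share when many were truly unchanged (as low as 0.44 in some runs), and to 0.70-0.83 when few were and dropout was unrelated to dose. These sizes rest on assumed dropout rates, mechanisms and baseline mixes.

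For the trial the effect is modest and mostly a false alarm: the larger placebo lowest category is diluted more, so a robust result may look slightly less so. The tipping-point value is blurred because part of the shift may be spent on impossible doses. The change should be made because it is cheap and because these checks are meant to test this endpoint. Nothing here puts the primary result in doubt.

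**What to change.** Impute r = dose/baseline by predictive mean matching. Replace each `monotone regression` statement with `monotone regpmm` on the ratio for that visit, with k=5. If the pattern is not monotone, use FCS REGPMM in place of the MCMC step. Drop the week-4 ratio as a predictor where it is constant at 1, because the dose is held during induction. Categorise the imputed fraction.

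Imputed fractions are then observed values, so no negative doses arise. In simulation the placebo lowest category came to 48% against a true 49%, 63% against 66%, 29% against 29% and 41% against 43%; under stronger dose-related dropout, 72% against 73%. Rounding to 2.5 mg with a floor at 0, or matching on mg, repaired only part of the loss (about 29-37% against a true 42-46%).

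For Appendix B, either convert back to mg (fraction × baseline), add the shift and then categorise, or restate the shift on the fraction scale.

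The cost is a few lines of SAP text and code before database lock, which the appendices already allow for by amendment. No data collection or patient is affected.

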2. To allow for MNAR in the reslizumab treatment group, a shift parameter will be used to adjust imputed values for OCS dose, by adding the shift parameter to the imputed values. The following pseudo-code is provided to demonstrate this concept, where OUTMI is the output dataset(s) from Step 1, COMPLETER identifies the patients who discontinued treatment early with incomplete follow-up, week24 is the OCS dose at week 24, and δ is the shift parameter.

```
data outmi;
  set outmi;
  if armcd='RESLIZUMAB' and COMPLETER='N' then week24=week24+ $\delta$ ;
run;
```

After this step, 10 datasets with complete data have been created.

3. The proportional odds model will be fitted to the complete set of data for each of the 10 datasets using the same covariates that were used for the primary analysis, following the outline described in [Appendix A](#) (Step 4).
4. Apply combining rules to the results from the 10 datasets using PROC MIANALYZE, as described in [Appendix A](#) (Step 5).
5. Repeat Steps 1-4 (above) using escalating values for the shift parameter resulting in estimates of the odds ratio and p-values for each shift parameter.

The odds ratio and associated p-value will be summarized corresponding to each selected shift value until the tipping point is achieved.

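### With only 10 imputations, the reported tipping-point shift carries appreciable Monte Carlo error, and a retrieved-data p-value close to 0.05 is imprecise

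*SAP*

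**What the plan says.** SAP Appendix A (Step 3) imputes the missing continuous OCS dose by sequential linear regression in PROC MI, coded with "nimpute=10 seed=&seed;". If the missing pattern is not monotone, a first MCMC call with the same setting makes it monotone, and a second call completes each dataset once. The text then confirms: "After this step, 10 datasets with complete data have been created". Step 1 fixes the seed beforehand, "resulting in a seed (49476) that will be used in the analysis after unblinding". Step 4 states that "Percent change from baseline and the corresponding 5-level response variable will be computed based on the imputed dose values at week 24", after which the proportional odds model is fitted to each dataset and the results are pooled.

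SAP Appendix B reuses these steps: "This process will be repeated 10 times". Placebo values stay as imputed under missing at random. For reslizumab, "a constant shift (>0) will be added to the imputed values", where "week24 is the OCS dose at week 24". The shift is raised until the treatment effect loses significance at the 5% level, and that shift is reported as the tipping point. The odds ratio and p-value are tabulated for each shift tried. The analysis runs only if the primary result has p of 0.05 or less.

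Neither appendix gives a Monte Carlo error check, a reason for choosing 10, or a grid of shifts.

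**The concern.** A pooled p-value from a finite number of imputations is itself an estimate: another set of draws from the same imputation model gives another value. When the p-value is only read as large or small, this seldom matters. Appendix B does more. It finds the shift at which p crosses a fixed line, so a small error in p can become a sizeable error in mg wherever p changes slowly with the shift.

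Appendix B then supports robustness if the tipping value is an unreasonable one. That judgement needs the value to be determined by the data and the model. If the same data could yield a small or a much larger shift depending on the draws, the judgement rests partly on chance. The retrieved-data analysis in Appendix A has the same weakness in milder form, and it shows only when its p-value lies close to 0.05.

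**Working it through.** **Inputs from the documents.** 10 imputations and the 5% crossing rule (SAP Appendices A and B). 76 patients per group, odds ratio 2.63, 90% power, and placebo category percentages 10.9, 7.9, 14.8, 10.8 and 55.6 (SAP 2.3). Two-sided 0.05 (SAP 4.3). Baseline dose 5 to 40 mg (Protocol 4.4). Treatment-period dose ladder (Protocol Table 3).

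**Assumptions.** The share of patients without week-24 data, the mix of baseline doses and the success of tapering are not in the documents. The simulated datasets had 8 to 19 imputed patients out of 152.

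**Step 1. Reproduce the plan's own figure.** Applying odds ratio 2.63 to the placebo percentages gives reslizumab percentages of 24.3, 13.5, 19.3, 10.6 and 32.3. The mean category probabilities are 0.176, 0.107, 0.170, 0.107 and 0.439, and their cubes sum to 0.0976. The Whitehead formula for n per group is

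6(1.960 + 1.282)² / [ln(2.63)² × (1 − 0.0976)] = 74.7.

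This rounds up to 75, and power at 76 is 90.5%. The stated 76 and 90% are reproduced, so the simulated trial matches the planned one in size and effect.

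**Step 2. Formula for the Monte Carlo error.** The standard deviation of the pooled z across seeds is about √(FMI/M), where FMI is the fraction of missing information and M the number of imputations. FMI is not the fraction of missing patients; in the simulated trials it was lower. Going from M = 10 to M = 100 divides the standard deviation by √10 = 3.2.

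**Step 3. Retrieved-data p-value.** The simulation used regression imputation with proper draws, a proportional odds fit and Rubin pooling. It drew 200 independent sets at M = 10 (central 95% shown) and 20 sets at M = 100 (minimum to maximum shown).

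| Imputed patients | FMI | True p | M = 10 | Seeds with p > 0.05 at M = 10 | M = 100 |
|---|---|---|---|---|---|
| 8 | 1.7% | 0.034 | 0.028–0.042 | – | 0.032–0.037 |
| 11 | 2.8% | 0.044 | 0.035–0.057 | 17% | 0.041–0.048 |
| 19 | 7.3% | 0.040 | 0.027–0.062 | 16% | 0.037–0.045 |

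Check of the last row by the formula: p = 0.040 is z = 2.054, and √(0.073/10) = 0.085. So z ± 2 SD is 1.88 to 2.22, or p = 0.026 to 0.060. With M = 100 the SD is 0.027 and p runs from 0.035 to 0.046. Both agree with the simulation.

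**Step 4. Tipping point at M = 10.** Three simulated trials were run with 60 independent sets of 10 imputations each, raising the shift in 0.5 mg steps.

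| Imputed patients (reslizumab) | p with no shift | Median tipping shift | Central 95% across seeds | Width |
|---|---|---|---|---|
| 11 (8) | 0.020 | 5.5 mg | 4.0–7.8 mg | 3.8 mg |
| 16 (10) | 0.012 | 5.0 mg | 4.0–6.5 mg | 2.5 mg |
| 16 (7) | 0.026 | 4.75 mg | 2.0–7.3 mg | 5.3 mg |

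These trials were picked because a tipping point exists in them: p was between 0.01 and 0.03 with no shift and above 0.055 at a very large one. The fitted model had treatment, OCS stratum and baseline dose, without age stratum or duration of OCS use. The tipping search was not repeated at M = 100. The expected gain there is the 3.2-fold reduction in Step 2.

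**Step 5. What a shift in mg means.** A 5 mg shift is 5/5 = 100% of a 5 mg baseline and 5/40 = 12.5% of a 40 mg baseline. From an imputed dose of 0, it moves the first patient from the top category to the bottom one, and the second only to an 87.5% reduction, one category down.

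**The case against.** The case against is substantial, and much of it stands.

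- **Fixed seed.** A reader might infer that the result could be steered by choice of seed. The documents do not support that: the seed is written into the SAP before unblinding, and the output is reproducible. What remains is imprecision.
- **Small missingness.** Patients who stop treatment but stay in the study contribute their own data, and Protocol 4.5.1 makes the week-24 OCS dose a priority assessment. With 8 imputed patients, the M = 10 range stays below 0.05.
- **Clear results do not flip.** At the design effect, expected z is about 3.24. Even at 10% missing information and M = 10, the SD is 0.10 and z of 3.04 to 3.44 gives p of about 0.0024 to 0.0006. Around p = 0.01 the range is 0.0055 to 0.0175. So it would be wrong to say that the retrieved-data conclusion depends on the seed in general.
- **The whole curve is reported.** This helps, but if the fixed seed is reused as written, every shift rests on the same 10 draws, so tabulating more shifts does not average the error out.
- **The mg scale.** One might call a constant mg shift an error. It is a choice: dose is imputed in mg, and two secondary endpoints use mg thresholds. A percentage shift has the opposite inequality, since 50% is 2.5 mg at a 5 mg baseline and 20 mg at 40 mg. Nor does it cure the seed spread: in the second trial of Step 4, the tipping value in percent of baseline still ranged from 27.5% to 45%.
- **An upper limit at 40 mg.** It is tempting to say that a 40 mg shift puts every shifted patient in the lowest category. It need not: the regression imputation has no lower bound. A 40 mg patient imputed at −3 mg and shifted by 40 mg is at 37 mg, a 7.5% reduction, which is not the lowest category.
- **A search without end.** If no shift tips the result, that shows robustness. The SAP leaves the reporting unstated, which is a detail and not a flaw in the method.

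**Conclusion.** The point holds for precision and is minor. Ten imputations are too few for a quantity defined by a p-value crossing: under the assumed dropout and dose mix, the reported tipping shift varied across seeds by about 2.5 to 5 mg around medians of 4.75 to 5.5 mg. The retrieved-data p-value is affected materially only when it is already close to 0.05. The actual size depends on how many patients lack week-24 data, which the documents do not state.

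The primary analysis uses no imputation and is untouched. A reader might take this point as doubt about the primary result, or as a claim that the robustness conclusion is generally unstable. The documents support neither.

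**What to change.** Set nimpute to at least 100 in the monotone call in SAP Appendix A Step 3 and in the first (MCMC) call of the non-monotone branch. Leave nimpute=1 in the second call of that branch, which completes each dataset once. Change the matching counts of 10 in Appendix A Steps 3 and 4 and in Appendix B steps 1 to 4. One hundred does not remove the error: near p = 0.05 with 10% missing information, ±2 SD is still 0.043 to 0.058, against 0.031 to 0.078 with 10 imputations. With 200 it is 0.045 to 0.055.

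Optional additions to Appendix B: report the tipping shift also as a percentage of baseline dose, and state that no tipping point exists if significance persists once all shifted reslizumab patients are in the lowest category.

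The cost is a small amount of computing time and a short edit. Both appendices already provide for an SAP amendment before database lock.
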